#### Confidential

Page 24 of 27

Version 1.3, Dec 04, 2019 Statistical Analysis Plan

-  Urine pregnancy test in women of childbearing potential only
-  Clinical safety labs include hematology, blood chemistry, and urinalysis at all visits. Please refer to laboratory manual for detailed schedule of tests.
-  Basic fasting lipids include total cholesterol (TC), calculated low-density lipoprotein cholesterol (LDL-C), high-density lipoprotein cholesterol (HDL-C), non-HDL-C,), and triglycerides (TG).
-  Only in patients receiving anticoagulant therapy that in the investigator's judgment require monitoring at Month 0 and 3 to 5 days post-Month 0
-  Interactive web response system (IWRS) contact at either an early withdrawal or an EOS visit to register study discontinuation visit date

# 8.2 Appendix 2: Adverse Event of Special Interest (AESI)

Adverse Event Terms per Protocol	Associated MedDRA Preferred Terms
Creatine kinase elevations	Blood creatine phosphokinase abnormal
Creatine kinase elevations	Blood creatine phosphokinase increased
Creatine kinase elevations	Blood creatine phosphokinase MM abnormal
Creatine kinase elevations	Blood creatine phosphokinase MM increased
New onset or worsening diabetes mellitus	Blood glucose abnormal
New onset or worsening diabetes mellitus	Blood glucose increased
New onset or worsening diabetes mellitus	Diabetes mellitus
New onset or worsening diabetes mellitus	Diabetes mellitus inadequate control
New onset or worsening diabetes mellitus	Diabetic ketoacidosis
New onset or worsening diabetes mellitus	Glucose tolerance impaired
New onset or worsening diabetes mellitus	Glucose urine present
New onset or worsening diabetes mellitus	Glycosuria
New onset or worsening diabetes mellitus	Glycosylated haemoglobin increased
New onset or worsening diabetes mellitus	Hyperglycaemia
New onset or worsening diabetes mellitus	Impaired fasting glucose
New onset or worsening diabetes mellitus	Ketoacidosis
New onset or worsening diabetes mellitus	Ketosuria
New onset or worsening diabetes mellitus	Ketosis
New onset or worsening diabetes mellitus	Type 2 diabetes mellitus
New onset or worsening diabetes mellitus	Urine ketone body present
Hepatic disorders	Alanine aminotransferase abnormal
Hepatic disorders	Alanine aminotransferase increased
Hepatic disorders	Aspartate aminotransferase abnormal
Hepatic disorders	Aspartate aminotransferase increased
Hepatic disorders	Blood bilirubin abnormal
Hepatic disorders	Blood bilirubin increased
Hepatic disorders	Hepatic enzyme abnormal
Hepatic disorders	Hepatic enzyme increased
Hepatic disorders	Hypertransaminaseaemia
Hepatic disorders	Liver function test abnormal
Hepatic disorders	Liver function test increased
Hepatic disorders	Transaminases abnormal
Hepatic disorders	Transaminases increased
Hypoglycemia	Blood glucose abnormal
Hypoglycemia	Blood glucose decreased
Hypoglycemia	Hypoglycaemia
Hypoglycemia	Hypoglycaemic coma
Hypoglycemia	Hypoglycaemic encephalopathy
Hypoglycemia	Hypoglycaemic seizure
Hypoglycemia	Shock hypoglycaemic
Metabolic acidosis	Metabolic acidosis
Muscular disorders	Muscular weakness
Muscular disorders	Muscle necrosis
Confidential	Page 26 of 27

Confidential

Page 26 of 27

Muscular disorders	Muscle spasms
Muscular disorders	Myalgia
Muscular disorders	Myoglobin blood increased
Muscular disorders	Myoglobin blood present
Muscular disorders	Myoglobin urine present
Muscular disorders	Myoglobinaemia
Muscular disorders	Myoglininuria
Muscular disorders	Myopathy
Muscular disorders	Myopathy toxic
Muscular disorders	Necrotizing myositis
Muscular disorders	Pain in extremity
Muscular disorders	Rhabdomyolysis
Neurocognitive/Neurologic disorders	Amnesia
Neurocognitive/Neurologic disorders	Cognitive disorder
Neurocognitive/Neurologic disorders	Confusional state
Neurocognitive/Neurologic disorders	Disorientation
Neurocognitive/Neurologic disorders	Memory impairment
Neurocognitive/Neurologic disorders	Mental status changes
Renal disorders	Acute kidney injury
Renal disorders	Acute prerenal failure
Renal disorders	Blood creatinine abnormal
Renal disorders	Blood creatinine increased
Renal disorders	Blood urea abnormal
Renal disorders	Blood urea increased
Renal disorders	Blood urea nitrogen/Creatinine ratio increased
Renal disorders	Creatinine renal clearance abnormal
Renal disorders	Creatinine renal clearance decreased
Renal disorders	Glomerular filtration rate abnormal
Renal disorders	Glomerular filtration rate decreased
Renal disorders	Gout
Renal disorders	Oliguria
Renal disorders	Prerenal failure
Renal disorders	Renal failure
Renal disorders	Renal function test abnormal
Renal disorders	Renal impairment

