- Hematology: Hematocrit (Hct), hemoglobin (Hgb), mean corpuscular hemoglobin (MCH), mean corpuscular hemoglobin concentration (MCHC), mean corpuscular volume (MCV), platelet count, red blood cell (RBC) count, white blood cell (WBC) count with differential (absolute values only)
- Urinalysis (Dipstick): Clarity, bilirubin, color, glucose, ketones, leukocyte esterase, nitrite, occult blood, pH, protein, specific gravity, urobilinogen

- Urinalysis (Microscopic): Obtain centrally only if positive urine dipstick; bacteria, casts, crystals, epithelial cells, RBC, and WBC
- Serum Chemistry (fasting): Albumin (ALB), alkaline phosphatase (ALK-P), alanine aminotransferase (ALT; or serum glutamic pyruvic transaminase [SGPT]), aspartate aminotransferase (AST; or serum glutamic oxaloacetic transaminase [SGOT]), blood urea nitrogen (BUN), calcium (Ca), carbon dioxide (CO₂), chloride (Cl), creatinine, creatine kinase (CK), glucose, lactate dehydrogenase (LDH), phosphorus, potassium (K), sodium (Na), total and direct bilirubin, total protein, uric acid
- HbA_{1C}

Safety and Monitoring:

Lipid results will be masked in order to maintain the blind from the parent study (1002-040) for the first 12 weeks of trial and unmasked after the Week 12 visit. See Section 10.1.4.4.1 for additional details.

Monitoring and Management of Potential AEs and Adverse Events of Special Interest (AESI)

Potential AEs:

Based on findings in nonclinical models, potential AEs include reversible hypoglycemia and metabolic acidosis. Potential cases of reversible hypoglycemia and metabolic acidosis will be identified by routine safety monitoring of AEs and clinical safety laboratories.

Musculoskeletal Safety:

Patients with CK abnormalities will also be reviewed for any other lab changes, such as creatinine, and any reported AEs or SAEs. Musculoskeletal events will be identified and evaluated by routine safety monitoring of PE findings and AEs.

Hepatic:

Hepatic function will be monitored throughout with the clinical safety labs. More detailed investigation will occur if the safety clinical laboratory results are 3 times or more than the upper limit of normal (ULN).

Further details on occurrence and monitoring are available in the Investigator's Brochure (IB) and protocol.

Statistical methods:

Sample Size

General Considerations

Statistical analyses in this open-label, multicenter single arm study will be descriptive in nature. No statistical inference is planned.

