10.1.4.4. Monitoring and Management of Potential Hypoglycemia and Metabolic Acidosis

Patients will be educated on the signs and symptoms of hypoglycemia. If such signs and symptoms are experienced, patients will be instructed to report these signs and symptoms to the investigator.

During each study visit, patients will be reminded to report all signs and symptoms associated with hypoglycemia to the investigator. For each occurrence of patient-reported signs and symptoms associated with hypoglycemia, the investigator will discuss these symptoms with the patient and assess whether they are attributable to hypoglycemia or to another potential cause. All investigator-confirmed occurrences of hypoglycemia will be recorded as an AE. All occurrences of signs and symptoms that are not confirmed by the investigator to be attributable to hypoglycemia will be reported using the appropriate diagnosis.

Clinical laboratories will be assessed to determine any signs of anion gap metabolic acidosis. If laboratories are consistent with metabolic acidosis, immediate follow up with the patient for further medical evaluation of the acidosis will occur. This event should be captured as an AE.

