11.3. Adverse Events of Special Interest

Adverse events of special interest (AESI) are included in this protocol for reasons either associated with other lipid lowering therapies or where deemed important based on nonclinical data. AESI for this protocol include: metabolic acidosis (clinical laboratories), hypoglycemia, muscular (AE and CK evaluation), hepatic, and neurocognitive/neurologic events.

Muscle: Muscle events have been associated with statins (Thompson 2003) and other lipidlowering therapies and are mentioned in the product information for these therapies. Muscle symptoms through AE review, CK elevations, and symptoms of potential myopathy will be closely monitored.

Hepatic: Hepatic function will be monitored throughout with the clinical safety labs. More detailed investigation will occur if the safety clinical laboratory results are $>3 \times$ ULN.

Neurocognitive Events: Theoretically, it is possible that lipid-lowering agents that disrupt cholesterol homeostasis in the brain could impact neurological function, and there have been reports of cognitive impairment (eg, memory loss) associated with the use of statin drugs

(FDA 2012). Summarization of events will occur using prespecified Medical Dictionary for Regulatory Activities (MedDRA) terms outlined in the statistical analysis plan (SAP).

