#### **5.4.4 Laboratory Evaluations**

Continuous laboratory parameters (serum chemistry, hematology, coagulation (only for those patients receiving anti-coagulation), urinalysis, urinalysis [microscopic]) listed in Table 4 will be summarized in conventional unit and SI unit using descriptive statistics at each scheduled visit starting from the baseline of the parent study. The similar completer analysis set approach for efficacy analysis described in section 5.3 will be used for selected parameters. Missing values for any of the laboratory evaluations will not be imputed; that is, only observed case data will be used.

Fasting serum glucose and HbA1c will be summarized using descriptive statistics for the observed value, change from baseline, and percent change from baseline at each scheduled visit by history of diabetics.

Categorical urinalysis data will be listed, but will not be summarized.

As part of the AESI evaluation, below safety lab abnormality will be summarized by treatment group. All post-baseline lab values during the on-treatment period are being considered. Further details are provided in Section 5.4.6.1 through 5.4.6.4.

- ALT or AST (>  $3 \times$  Upper limit of normal (ULN) and > $5 \times$  ULN)
- Total bilirubin (TB) (> 2 × ULN)
- Potential Hy's Law case: (ALT and/or AST > 3 × ULN with concurrent TB > 2 × ULN)
- CK (>  $5 \times$  ULN) and (> $10 \times$  ULN)
- Fasting Serum Glucose (mg/dL) ( $\leq$  50, and  $\geq$  126) by history of diabetics
- HbA1C ( $\geq$  6.5%) by history of diabetics
- Creatinine (change from baseline for >1 mg/dL)
- eGFR (< 15 mL/min/1.73m^2, 15 29 mL/min/1.73m^2)
- Hgb (g/dL) (decrease from baseline for  $\geq 2$  g/dL)
- Hgb (< 8 g/dL)

The number and percentage of patients with the following laboratory abnormalities will be summarized by the parent study baseline statin intensity, previous treatment group in the parent study, and overall in the OLE study:

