#### Confidential

Page 18 of 27

- ALT or AST (>  $3 \times$  ULN and > $5 \times$  ULN)
- TB (>  $2 \times ULN$ )
- Potential Hy's Law case: (ALT and/or AST >  $3 \times$  ULN with concurrent TB >  $2 \times$  ULN)
- CK (>  $5 \times ULN$ ) and (> $10 \times ULN$ )
- Creatinine (change from baseline for > 1 mg/dL)
- eGFR (< 15 mL/min/1.73m^2, 15 29 mL/min/1.73m^2)
- Hgb (g/dL) (decrease from baseline for  $\geq 2$  g/dL)
- Hgb (< 8 g/dL)

For labs of interest (such as uric acid, hemoglobin, creatinine, BUN, and Fasting glucose by diabetes history), a line plot will be generated to visualize the mean values over time.

A matrix display of liver dysfunction shift from baseline to maximum value will be used to visualize the abnormal values of labs including AST, ALK-P ALT, and TB.

Table 2:	Clinical Laboratory Parameters (Safety)
----------	---

Clinical Laboratory Test	Clinical Laboratory Test
• Hematology	Blood Chemistry (serum, fasting)
• Hematocrit (Hct)	• Albumin (Alb)
• Hemoglobin (Hgb)	• Alkaline phosphatase (ALK-P)
• Mean corpuscular hemoglobin (MCH)	• Alanine aminotransferase (ALT; SGPT)
• Mean corpuscular hemoglobin	• Aspartate aminotransferase (AST;
concentration (MCHC)	SGOT)
• Mean corpuscular volume (MCV)	• Blood urea nitrogen (BUN)
• Platelet count	• Calcium (Ca)
• Red blood (RBC) cell count	• Carbon dioxide (CO2)
• White blood (WBC) cell count with	• Chloride (Cl)
differential (absolute and %)	• Creatinine
Urinalysis (Dipstick)	• Creatine kinase (CK)
• Clarity	• Glucose
Bilirubin	• Lactate dehydrogenase (LDH)
• Color	Phosphorus
• Glucose	• Potassium (K)
• Ketones	• Sodium (Na)
• Leukocyte esterase	• Total and direct bilirubin (TB)a
• Nitrate	• Total protein
Occult blood	• Uric acid
• pH	Coagulation—only in patients receiving
• Protein	anticoagulant therapy that in the investigator's
• Specific gravity	judgment require monitoring at Month 0 and
• Urobilinogen	3 to 5 days post-Month 0
-	Prothrombin time
	• International normalized ration (INR)
Urinalysis (Microscopic)-only if urine dipstick	Other Labs:
abnormal	• Urine pregnancy test
• Bacteria	• Hemoglobin A 1C (HbA 1C )
• Casts	
Crystals	
• Epithelial cells	
• RBC	
• WBC	

 $^{\rm a}\,$  If TB  ${\geq}1.2 \times$  ULN, a reflex indirect (unconjugated) bilirubin will be obtained.

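### Metabolic acidosis is an AESI that the protocol assesses by laboratories, but SAP v1.3 gives it no laboratory item and one preferred term, so some cases would not be counted under that AESI

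*SAP*

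**What the plan says.** The protocol treats metabolic acidosis as a risk named in advance from nonclinical findings. Its synopsis gives two routes of detection: "Potential cases of reversible hypoglycemia and metabolic acidosis will be identified by routine safety monitoring of AEs and clinical safety laboratories". Section 11.3 puts it among the AESI and states how it is assessed: "AESI for this protocol include: metabolic acidosis (clinical laboratories), hypoglycemia, muscular (AE and CK evaluation), hepatic, and neurocognitive/neurologic events". Section 10.1.4.4 is more specific: "Clinical laboratories will be assessed to determine any signs of anion gap metabolic acidosis". It then requires immediate follow-up of a patient whose laboratories fit the diagnosis and adds: "This event should be captured as an AE". No numeric limit is given.

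SAP v1.3 section 5.4.2 identifies AESI from the preferred terms in Appendix 2 and says that AESI are also evaluated on safety laboratory parameters. (It points to section 5.4.5 for these; in v1.3 the laboratory material is in 5.4.4.) Section 5.4.4 introduces the list as follows: "As part of the AESI evaluation, below safety lab abnormality will be summarized by treatment group". The list covers liver enzymes, bilirubin, Hy's law, CK, fasting glucose, HbA1c, creatinine, eGFR and hemoglobin. In Appendix 2 the metabolic acidosis group holds one preferred term, "Metabolic acidosis".

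**The concern.** Long-term safety is the primary objective, and this risk was named before the study began. For liver, muscle, kidney and glucose, the SAP pairs adverse-event terms with a programmed laboratory count, so the laboratory data can act as a check on what investigators chose to report. For metabolic acidosis, which the protocol ties to laboratories, that check is absent. The AESI result then depends on investigators at about 125 sites recognizing the pattern without a stated limit and reporting it, and on the report being coded to exactly one term. A reader of the study report who looks up this AESI would see only the events that passed both steps.

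**Working it through.** The plan states no figure to reproduce, and no power or interval calculation applies. The check is a count of what SAP v1.3 provides, followed by tracing where each kind of case would appear.

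**1. AESI laboratory list (SAP v1.3, 5.4.4).** There are ten bullets: ALT or AST, total bilirubin, potential Hy's law, CK, fasting glucose, HbA1c, creatinine change, eGFR, hemoglobin decrease, hemoglobin below 8 g/dL. Items for CO2, chloride or anion gap: 0 of 10. The dedicated subsections 5.4.4.1 to 5.4.4.4 cover hepatic, musculoskeletal, glycemic and renal safety only.

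**2. The paired risk.** The protocol handles hypoglycemia and metabolic acidosis together, in the synopsis and in section 10.1.4.4. Hypoglycemia has a laboratory cut-off in the list (fasting glucose at or below 50 mg/dL). Acidosis has none, and no reason is given.

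**3. Appendix 2 rows by group (v1.3).** CK elevations 4, diabetes 16, hepatic 13, hypoglycemia 7, metabolic acidosis 1, muscular 14, neurocognitive 6, renal 17.

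4 + 16 + 13 + 7 + 1 + 14 + 6 + 17 = 78, so acidosis has 1 row of 78. The hepatic and renal groups include laboratory-type terms (for example, raised ALT or creatinine); the acidosis group has none. Three related terms (Diabetic ketoacidosis, Ketoacidosis, Ketosis) sit only under diabetes, or five with the two urinary ketone terms. The appendix does allow a term in two groups: Blood glucose abnormal is under both diabetes and hypoglycemia.

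**4. Where each kind of case would appear under SAP v1.3.**

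| Case | Counted as the metabolic acidosis AESI? | Where else it appears |
|---|---|---|
| Reported as an AE, coded Metabolic acidosis | Yes | All TEAE tables and listings |
| Reported as an AE, coded to a term not in Appendix 2 | No | TEAE tables by SOC and PT; AE listing |
| Reported as Ketoacidosis or Diabetic ketoacidosis | No; grouped as diabetes | By name in the AESI tables (by SOC and PT) and in the TEAE tables |
| Laboratory pattern only, not reported as an AE | No | CO2, Na and Cl each summarized by visit and counted when out of range; anion gap nowhere |

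**5. What the general laboratory table can show.** Section 5.4.4 counts values outside the normal range, one parameter at a time and by time point, including unscheduled tests. It does not say that low and high CO2 are separated, does not combine Na, Cl and CO2, and does not specify a count of patients with the finding at any post-baseline time. It therefore cannot show an anion gap acidosis.

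**6. Scale.** Expected enrolment is about 1300 (protocol synopsis). One patient is 1/1300 = 0.08%. This is the resolution of the AESI table, not an estimate of how many cases are affected.

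**The case against.** The strongest reply is that the design is laboratory detection followed by an AE-based summary. Protocol 10.1.4.3 has the investigator review every laboratory result, 11.1.3 requires clinically significant abnormalities to be reported as AEs, and 10.1.4.4 requires laboratory-consistent acidosis to be recorded as an AE. The superseded SAP v1.0 (section 5.4.2) described acidosis in the same way: monitored by laboratories, summarized from AEs. Protocol section 12.6 specifies hepatic, muscle, glycemic, renal and neurocognitive summaries but no acidosis laboratory table. A reader might infer that SAP v1.3 breaks a promised analysis. The documents do not support that, and this part of the reply stands.

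A reader might also infer that acidosis cases are missed, or that laboratory-only cases are counted nowhere. Neither is supported. Reported events stay in the TEAE tables and listings, ketoacidosis is visible by name in the AESI tables, and CO2 has by-visit statistics and out-of-range counts. Grouping ketoacidosis with diabetes is medically defensible; cross-listing it is only a labelling gain.

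The reply does not remove the gap in the AESI count itself. The reporting route has no stated limit and varies by investigator. A programmed laboratory summary would show under-reporting, and the SAP supplies one for the other laboratory-based AESI.

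**Conclusion.** The point holds in a limited form. SAP v1.3 evaluates AESI on laboratory parameters but includes no acidosis item, and it identifies this AESI by one preferred term. A laboratory-only case not reported as an AE, or an acidosis AE coded to another term, would not be counted as the metabolic acidosis AESI. The size cannot be computed, because neither document gives an acidosis incidence; the number of affected patients may be zero. The study is descriptive, so no test or decision rule changes.

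A reader might go further and conclude that the report could falsely declare the study free of acidosis. That would require the report's author to overlook named rows in the AESI and TEAE tables or the CO2 abnormality counts, and the documents give no ground for assuming it.

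The conclusion assumes that the final analysis follows SAP v1.3, which states that it supersedes the protocol on data analysis, and that the general abnormality table is produced as worded. It is a worthwhile improvement on a risk named in advance, not a flaw that undermines the safety analysis.

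**What to change.** Add two items to the AESI laboratory list in SAP section 5.4.4:

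- The number and percentage of patients with CO2 below the central laboratory's lower limit of normal, by visit and at any on-treatment post-baseline time.
- The derived anion gap, Na - Cl - CO2: value and change from baseline by visit, and the number of patients above an analysis limit that the sponsor specifies and justifies before database lock. Show also the patients who meet both criteria. The documents supply no limit, and none is proposed here.

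In Appendix 2, list Ketoacidosis and Diabetic ketoacidosis under metabolic acidosis as well as diabetes, as is already done for Blood glucose abnormal.

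The cost is SAP wording, one derived variable and one or two tables. Na, Cl and CO2 are already in Table 2, so no sample, visit or form changes. The downside is some non-specific flags, since low CO2 or a raised gap in a single sample need not be acidosis; a footnote can say so.

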#### 5.4.1 Adverse Events (AEs)

AEs will be coded using the Medical Dictionary for Regulatory Activities (MedDRA) Version 20.1 or later and will be categorized by system organ class (SOC) and preferred

Confidential

Page 15 of 27

Page 117 of 129

term (PT). Summary tables will focus on TEAEs; however, listings will include all AEs (with non-TEAEs flagged). An additional AE listing will be provided for AEs occurred during rollover period.

In summary tables, TEAEs will be counted as "Not Related" if relationship to study drug was recorded as 'Not Related' or "Unlikely". Events will be counted as "Related" if relationship to study drug was recorded as 'Possible', 'Probable', 'Definite' or if relationship to study drug is missing.

The severity of the AE will be characterized as mild, moderate, or severe, to the following definitions:

- Mild: Events are usually transient and do not interfere with the patient's daily activities
- Moderate: Events introduce a low level of inconvenience or concern to the patient and may interfere with daily activities
- Severe: Events interrupt the patient's usual daily activity, are incapacitating with inability to do usual activities, or significantly affect clinical status and warrant intervention and/or close follow-up

Overviews of TEAEs will include total number of TEAEs, and patient incidence of TEAEs, TESAEs, treatment-related TEAEs, treatment-related TESAEs, IMP withdrawal due to TEAEs, TEAEs with fatal outcome. Individual TEAE summary will be presented by previous treatment group in parent study and overall containing the following counts and percentages for:

- patients with TEAEs by SOC and PT
- patients with TEAEs by PT
- patients with TEAEs by SOC, PT, and maximum severity
- patients with treatment-related TEAEs
- patients with treatment-related TEAEs by PT
- patients with treatment-related TEAEs by SOC and PT
- patients with treatment-emergent serious adverse events (TESAEs) by SOC and PT
- patients with TESAEs by PT
- patients with TESAEs by SOC, PT, and maximum severity
- patients with treatment-related TESAEs
- patients with treatment-related TESAEs by SOC and PT
- TEAEs leading to withdrawal of IMP by SOC and PT
- fatal TEAEs by SOC and PT

Preferred terms for TEAEs that occurred in more than 1% of subjects overall will be plotted using the overall group. This plot will be repeated for TESAEs in the overall group.

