#### Confidential

Page 16 of 27

In addition, summary tables will be provided, by prior treatment group and overall, for the number and percent of patients experiencing:

- adjudicated major adverse cardiovascular events and mortality (MACE) by event type
- non-CV deaths (non-MACE),
- nonfatal myocardial infarction [MI] (MACE),
- nonfatal stroke (MACE),
- hospitalization for unstable angina (MACE),
- coronary revascularization (MACE),
- noncoronary arterial revascularization (non-MACE),
- hospitalization for heart failure (non-MACE) using standardized definitions.

The TEAE, treatment-related TEAE, TESAE, and AESI summaries by SOC, PT and maximum severity will be provided for relevant subgroups described in 5.2.5 with the exception of baseline LDL category.

The AE overview summaries will count a patient at most once in each AE category (at the "highest/most extreme" designation of each category regardless of preferred term) and percentages will be based on the total number of patients in the safety population.

In addition to a comprehensive listing of all AEs (with non-TEAEs flagged), separate listings will be generated for serious adverse events, TEAEs resulting in withdrawal of study drug, and TEAEs with a fatal outcome, investigator reported major adverse cardiovascular events and mortality, and adjudicated major adverse cardiovascular events and mortality.

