#### 5.4.2 Adverse Events of Special Interest

Adverse events of special interest (AESI) will be identified based on a pre-defined list of preferred terms provided by the sponsor (Appendix 2).

AESI will be presented in a listing and summarized by SOC, PT, and previous treatment group in parent study and overall in OLE study. A separate table for treatment-emergent AESI resulting in the discontinuation of study drug will be summarized by SOC, PT, and previous treatment group in the parent study and overall in OLE study.

In addition to adverse events, AESI is also being evaluated based on safety lab parameters. The details are provided in 5.4.5.

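### A misspelled muscular term in SAP Appendix 2 would, if the list is applied as printed, drop myoglobinuria events from the AESI outputs, though not from the general adverse event tables

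*SAP*

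**What the plan says.** SAP v1.3, section 5.4.2, states that AESI "will be identified based on a pre-defined list of preferred terms provided by the sponsor (Appendix 2"). Appendix 2 (section 8.2) is a two-column table. The left column gives the AESI category and the right column, headed "Associated MedDRA Preferred Terms", gives the terms that define it. Under Muscular disorders one of the terms is "Myoglininuria". Among its neighbours are "Myoglobin urine present", "Myoglobinaemia" and "Rhabdomyolysis". The same misspelling stands in Appendix 2 of SAP v1.1 and v1.2.

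Section 5.4.2 uses the list for an AESI listing, a summary by system organ class and preferred term, and a separate table of treatment-emergent AESI that led to discontinuation of study drug. Section 5.4.1 adds AESI summaries by maximum severity within the subgroups of section 5.2.5, except baseline LDL category.

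Other outputs do not use the list. Section 5.4.1 tabulates "patients with TEAEs by SOC and PT", and its paragraph on listings begins "In addition to a comprehensive listing of all AEs (with non-TEAEs flagged"). Section 5.4.4.2 summarizes creatine kinase from laboratory values.

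**The concern.** In most places a misspelling in a SAP is cosmetic. Here the word belongs to a list that decides which coded events count as AESI. A selection that finds nothing for one entry looks the same as a selection for an event that nobody had, and the SAP contains no step that would tell the two apart: no preferred-term codes, no stated matching rule and no check of the list against the dictionary. SAP v1.0 had the clinical team help to pull AESI out of the database. From v1.1 the section 5.4.2 text relies on the list alone.

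Muscle safety is not a side issue in this study. Protocol section 11.3 names muscular events as an AESI, and section 4.2.1 says that long-term safety for skeletal muscle has still to be established. The safety laboratory panel in SAP Table 2 includes creatine kinase but no myoglobin assay. Within the AESI evaluation, myoglobinuria can therefore be picked up by name only through the term list. At stake is whether the muscular AESI tables hold every event that they were meant to hold.

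**Working it through.** No sample size, power or error rate bears on this point, and the plan states no figure to reproduce. The check is on the list itself.

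1. **Is it a true misspelling?** The string is identical in Appendix 2 of v1.1, v1.2 and v1.3, which makes a fault in reading the PDF unlikely. It stands between "Myoglobinaemia" and the myopathy terms, in a column reserved for MedDRA preferred terms. The intended word is evident.

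2. **How much of the muscular category is affected?** The 14 entries under Muscular disorders in v1.3 were compared with the intended spelling, first exactly and then ignoring case.

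| Term sought | Found in the list |
|---|---|
| Myoglobinuria | No |
| "Myoglobin urine present" | Yes |
| "Myoglobinaemia" | Yes |
| "Rhabdomyolysis" | Yes |

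Five of the 14 entries concern myoglobin: two blood-myoglobin findings, the urine-myoglobin finding, myoglobinaemia and the misspelled one. Four of those 5 are usable as printed, and 5 of 5 would be after correction. For the whole category the unusable share is 1/14, or about 7% of entries. That is a share of terms, not of events.

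3. **Which outputs depend on the list?** The AESI listing, the AESI table by system organ class and preferred term, and the AESI-leading-to-discontinuation table (section 5.4.2), and the subgroup AESI summaries (section 5.4.1). Section 5.2.5 names 9 subgroup variables and one is excluded for safety, so 9 − 1 = 8 variables are in scope, subject to the small-subgroup rule. The Day 120 addendum repeats AESI tables under the SAP of 5 December 2018 (v1.2), which has the same entry, so the same condition applies there.

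4. **Which outputs do not?** The all-TEAE tables by preferred term, the serious, withdrawal and fatal TEAE tables, the full adverse event listing and the creatine kinase laboratory summaries.

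5. **How many events would be missed?** This cannot be computed. Neither document gives any adverse event count.

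**The case against.** The strongest reply is that the loss is only potential. Section 5.4.2 says the list is the basis for identification. It does not say that events are matched by literal text. A programmer may work from MedDRA codes, or may notice the slip and correct it. This stands, and it is why the point is conditional.

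A second reply is that the event would remain visible. It would appear under its own name in the all-TEAE table and in the listing, and in the serious or withdrawal tables if it qualified. Creatine kinase above 5 and above 10 times the upper limit of normal is summarized whatever the term list says. A patient with any other listed muscular term would still be counted as having a muscular AESI. All of this stands and limits the consequence.

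A reader might infer that a rhabdomyolysis marker is certain to vanish from every AESI table. The documents do not support that: no matching rule is stated, "Rhabdomyolysis" and "Myoglobin urine present" are both listed correctly, and only one term is in question. A reader might also want to attach an upper confidence limit to a zero count for the term. No such limit is planned. Protocol section 12.1 plans no inference, and SAP v1.3 section 5.1 confines confidence intervals to selected continuous endpoints.

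What the replies do not remove is the error itself. If the tables come out right only because someone repairs the list while programming, the selection rule was not fully specified in advance.

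**Conclusion.** The point holds as a minor, conditional specification error in an operative list. If Appendix 2 is applied as printed, 1 of 14 muscular terms selects nothing, and an event coded to the intended term is omitted from the four kinds of AESI output named above. It is not omitted from the report: the general TEAE tables and the full listing would show it. The primary endpoint, the efficacy summaries and the creatine kinase analyses are unaffected.

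This rests on two assumptions. The first is that the list is used as literal text, which the SAP neither states nor excludes. The second is that the coded preferred term is spelled *Myoglobinuria*. The neighbouring entries make this the evident intention, but the dictionary is not among the documents. For the same reason, nothing is claimed here about the validity of any other entry. Whether any patient had such an event is unknown, so the effect on the reported counts may be nil.

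**What to change.** - In Appendix 2, under Muscular disorders, correct the entry to *Myoglobinuria*.
- In section 5.4.2, add that before database lock every Appendix 2 term is merged against the MedDRA version used for coding, and that any term without a match is corrected and reported. Naming that version matters because section 5.4.1 says only version 20.1 or later.
- Preferably print the preferred-term codes beside the terms and state whether matching is by code or by text.

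The cost is one word, a sentence or two and one dictionary merge. No endpoint, population or planned table changes. AESI counts would change only if an event had been coded to a corrected term. If the Day 120 AESI tables were run from the list as printed, the same check should be repeated on them and any difference noted in the study report.
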